### 13. Disclosure of PHI to a collaborator

If any data will be sent outside of this site, list each recipient (may list by role or category if the information is the same for several different entities). For each recipient, describe:

- The name and location of the individual/entity receiving the information.

N/A

- What information and/or biospecimens will be sent.

N/A

- Whether the information will be fully identifiable (PHI, if health information), a Limited Data Set, de-identified, or aggregate.

N/A

- How the data/materials will be transferred securely (for instance, Secure File Transfer). Indicate if hard copy PHI will be stored/sent to a collaborator.

N/A

- When applicable, clarify whether there are written assurances from collaborators that PHI will not be reused or re-disclosed to any other entity. Describe assurances that PHI will be stored securely.

N/A

#### 14. Provisions to Monitor Data to Ensure the Safety of Subjects

This is required when research involves more than Minimal Risk to subjects.

The plan might include establishing a data monitoring committee and a plan for reporting data monitoring committee findings to the IRB and the sponsor. Describe:

- Who will monitor the study data for safety?

The PIs will review all safety data collected at the 3-month (T1) and 6-month (T2) follow-up surveys.

- The plan to periodically evaluate the data collected regarding both harms and benefits to determine whether subjects remain safe.

The PIs will review reported adverse events collected at the 3-month (T1) and 6-month (T2) follow-up surveys every 6 months during data collection.

- What data are reviewed, including safety data, untoward events, and efficacy data.

We will collect data on severe or life-threatening injury or illness that required hospitalization overnight in postpartum participants or their infants, whether adverse events were related to exercise, and whether adverse events resulted in persistent or significant disability or incapacitation.

- How the safety information will be collected (e.g., with case report forms, at study visits, by telephone calls with participants).

Adverse event information will be reported by participants as part of follow-up surveys.

- The frequency of data collection, including when safety data collection starts.

Adverse event information will be collected as part of the 3-month and 6-month follow-ups surveys.

- The frequency or periodicity of review of cumulative data.

Adverse event data will be reviewed by the PIs every 6 months during data collection.

- Criteria for taking action on monitoring findings (for instance, stopping rules, immediate suspension, reporting, protocol changes, changes to monitoring frequency or plan).

Serious adverse events are not anticipated in this study. If serious adverse events (adverse events that require hospitalization or results in a persistent or significant disability or incapacitation in the postpartum participant or her infant) are reported related to exercise, the PIs will report these events to the IRB and remove participants who experience serious adverse events from the study. The PIs will incorporate protocol changes, including increasing adverse event monitoring to include identification of hospitalization events in participants using the electronic health records on a more frequent basis (i.e. monthly).

- For studies monitored by a DSMB/C, describe the committee membership and structure, meeting format, and quorum requirements. Upload the board/committee charter, if one exists.

N/A

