- Describe the plan for disposition of information/biospecimens collected during recruitment/screening in the event of a screen failure or when a potential subject is contacted but declines participation (e.g. destroyed immediately, destroyed at end of study, retained for separate analysis or so that subjects are not contacted repeatedly about participation after they have declined, etc.).

Data collected during recruitment/screening or when a potential subject is contacted for participation but declines will be destroyed at the end of the study. Subjects will not be contacted about participation after they have declined.

Non-respondent data will be used in the study. Any collected data will be destroyed at the end of the study.

For those who decline to have their data be used for this study, any collected data will be destroyed at the end of the study.

c. Subjects Vulnerable to Coercion or Undue Influence

Indicate whether you will include or exclude each of the following special populations. Justify the inclusion of any of these populations. Describe additional safeguards to protect the rights and welfare of these subjects. Note: This refers to subjects who are known members of these populations upon enrollment or at any time during the study.

- Children

We will include children in the proposed study. We will need to access and link records for each enrolled mother/baby to extract data regarding the pregnancy and other health factors including child development and behavioral problems, maternal-infant interaction, and breastfeeding for 3 reasons: 1) inclusion/exclusion criteria (i.e. we cannot recruit women with infants that have a chronic illness and thus need to access their medical records), 2) to assess the relationships as outlined in the Aims, and 3) monitor adverse events and safety outcomes (e.g. identify any injuries that may have been treated by a doctor or required hospitalization and follow-up and their relationship with the intervention).

Only persons directly involved in the study will have access to the data identifying individual participants. Names of participants will be obtained for record-keeping purposes

only; no names will be recorded in the data analysis files. No individuals will be identified in the results of the studies. Access to computer-stored information will require simultaneous knowledge of the data format, computer language, file name, and password.

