- c. Explain how the research presents no more than minimal risk of harm to these subjects
- d. Provide an appropriate alternative mechanism for documenting that informed consent is obtained

Click or tap here to enter text.

d. Alteration of Informed Consent

Identify the required elements of informed consent that you wish to remove or alter.

N/A

Provide justification for their removal or alteration.

Click or tap here to enter text.

e. Non-English-Speaking Subjects

If subjects who do not speak English will be enrolled, describe how the consent discussion will take place and indicate if translated consent forms or short forms will be used. Confirm that an interpreter will assist with the initial consent process and subsequent study visits.

N/A

**IMPORTANT NOTE:** Please be aware that if it is expected that you will enroll non-English speakers in the study, short forms should not be used as the only Consent option for these individuals, they should only be used if a non-English speaking participant is unexpectedly encountered. However, the possibility of encountering non-English speaking potential subjects in the Bay Area is a possibility and this possibility should be considered, and budgeted for, when preparing the initial study submission for IRB review.

f. Assent of Children and Parent Permission

**IMPORTANT NOTE:** Child Consent may be obtained in certain situations (for example, conducting family planning or sexually transmitted disease (STD) research). In addition, for older children ages 16 and up who participate in an adult study, the consent document can be used in place of the assent document.

Describe how you will obtain and document assent/parental permission, including:

- Describe your plan for obtaining parent permission. The permission of one parent is generally sufficient for minimal risk research, or for greater than minimal risk research if there is the potential for direct benefit to the child. For studies involving greater than minimal risk with no prospect of direct benefit to the child, permission of both parents is required unless one parent is deceased, unknown, incompetent, or not reasonably available, or when only one parent has legal responsibility for the care and custody of the child.

**Aim 1:** Parent permission will be obtained for accessing child records and child assent will not be obtained.

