**9. Study Procedures**

## a. Description

Describe and explain the study design, including:

- A detailed chronological description of all research procedures.

This is a hybrid effectiveness-implementation study including 1) a randomized controlled trial to test the effectiveness of MomZing to increase physical activity and reduce postpartum depressive symptoms in women at increased risk of PPD and 2) evaluation of implementation of MomZing within the KPNC health care delivery system. We will identify potential participants and assess them through clinician referrals and using KPNC's electronic health records data for eligibility. All eligible and recruited women will complete a baseline survey including self-report of PA and wear a research-grade accelerometer for 7 continuous days to assess baseline PA. We will mail the accelerometer and wearing instructions, and also provide a self-addressed prepaid postage envelope for participants to return the items after each measurement period. All participants will be informed that they do not have to answer any question in the surveys they do not wish to answer. We will then randomize 200 women into 1 of 2 arms: 1) Intervention (MomZing, n=100) or 2) Control (Usual care, n=100) using a restricted randomization scheme to ensure an acceptable level of between-arm balance in the distribution of important covariates (e.g. KP clinic, race/ethnicity, age, parity, marital status, and education). The nature of the group assignment and intervention does not allow for blinding of the treatment conditions from the participant or the research assistant whose task is to register and explain the use of the MomZing intervention. The programmer/analyst, biostatistician, and investigators will be blinded to the study arms. Once randomized, participants will begin their assigned group's intervention or control treatment for 3 months. We will obtain both self-report and accelerometer-measured PA and depressive symptoms at 3 months (T1) and 6 months (T2) post-baseline for each woman in their respective arms. There will be one final survey when the participant's child is 12 months old to assess child development. Non-respondent data will be used for those who do not respond to the recruitment emails and calls. They will be given 30 days to opt out of the study and informed that their data may be used if they do not respond.

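### Section 5c plans to use linked records for adverse-event monitoring, but Section 14 names only participant surveys, and no routine record check is described

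*Combined protocol and SAP*

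**What the plan says.** Section 5c, under Children, explains why the study must "access and link records for each enrolled mother/baby to extract data". It gives three reasons. The third is safety monitoring, and its example is to "identify any injuries that may have been treated by a doctor or required hospitalization and follow-up and their relationship with the intervention".

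Section 14 is where the plan states how safety data are gathered. On the method it says: "Adverse event information will be reported by participants as part of follow-up surveys". The collection times are the 3-month (T1) and 6-month (T2) surveys. On content it says: "We will collect data on severe or life-threatening injury or illness that required hospitalization overnight in postpartum participants or their infants", and it adds whether events were exercise-related and whether they caused lasting disability. Its definition of a serious event is worded differently: "adverse events that require hospitalization or results in a persistent or significant disability or incapacitation in the postpartum participant or her infant", without the overnight condition. The EHR appears once. If exercise-related serious events are reported, the protocol changes are to extend monitoring to "identification of hospitalization events in participants using the electronic health records on a more frequent basis (i.e. monthly".

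Section 9a ties the PIs' 6-monthly safety review to the T1 and T2 surveys. It also has the research assistant, project manager and programmer look at adverse-event data every 6 months, without saying where those data come from.

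**The concern.** Two sections give different accounts of the source of adverse-event data and of the least serious event that counts. Staff working from Section 5c would search linked records for treated injuries. Staff working from Section 14 would rely on survey answers, and on a description of injury and illness limited to overnight stays. Event counts could therefore depend on which section is followed.

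Section 15a names ankle sprains and muscle strains as foreseeable in the intervention arm. Such injuries can be treated without admission, so they fall within Section 5c's example but may fall outside Section 14's description. Infants take part in the workouts and cannot report for themselves; under Section 14 they are covered only through the mother's survey. The records that could show treated events among women who do not return a survey are, as described, searched only after an exercise-related serious event has already been reported.

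**Working it through.** The plan gives no figure on this point and no arithmetic applies, so the check is a comparison of every section that deals with adverse events, injuries, hospitalization or EHR data.

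1. **Source.** Section 5c: linked mother and infant records. Section 14: participant report at T1 and T2. Section 9a: T1 and T2 survey data for the PIs' review; source unstated for the study team's review. No section connects the record-based purpose to the survey-based procedure.

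2. **Threshold.** Section 5c: injuries treated by a doctor or needing hospitalization, given as an example. Section 14: injury or illness with an overnight stay. Its two further items, exercise-relatedness and disability, carry no overnight limit, but doctor-treated injury without admission is never named there.

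3. **Wording within Section 14.** The description of data collected requires an overnight stay. The serious-event definition requires only hospitalization.

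4. **Record check.** The only adverse-event search of the EHR with a stated frequency is the conditional one in Section 14. It is monthly, covers hospitalizations only, and follows a reported exercise-related serious event. Its reference to a more frequent basis hints at an existing, less frequent check. But the sentence presents the search as something monitoring is increased to include, which reads as an addition. No baseline check is described anywhere.

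5. **Other EHR use.** Section 9a lists EHR databases among the study's data sources and takes health care utilization partly from them. That is described as a study measure, not as safety monitoring, and has no safety schedule.

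6. **Consequence of following Section 14 literally.** A woman who returns neither survey contributes no adverse-event report for herself or her infant, even if an injury was treated and recorded. A woman who misses T1 might still report the event at T2, depending on the recall period asked about. Whether a treated sprain without admission is captured depends on the survey items in Appendices M-P, which were not available.

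**The case against.** The strongest reply is that the sections are complementary. Section 5c justifies including children and offers its threshold only as an example; Section 14 answers template prompts. The hint of an existing check, the unrestricted source of the study team's review and the EHR's place among the data sources all fit a plan in which records are consulted routinely. This reading is possible, and a reader who infers outright contradiction goes further than the text allows. It does not close the gap, because a routine check that is nowhere described cannot be relied on to happen.

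A reader might also infer that sprains and strains will certainly be missed. The documents do not support that: only one item in Section 14 carries the overnight limit, and the survey questions are unseen.

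A third temptation is to turn the 16% loss to follow-up in Section 9b into a count of women without safety reports. That figure is an allowance in the power calculation, not a survey non-return rate. The plan also has reminders (Section 6) and payments (Section 17) to support survey return.

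Two limits on the remedy stand. Records miss care received outside KPNC, and eligibility requires KPNC prenatal care and delivery but not continued membership. Nor do records remove the influence of knowing one's arm, since that can affect care-seeking as well as reporting.

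**Conclusion.** The point holds as a minor one. The plan states a record-based safety purpose in Section 5c and a survey-only procedure in Section 14, does not reconcile them, and describes no routine record check. If Section 14 is followed as written, treated injuries in women who do not return a survey stay outside safety monitoring. Treated injuries without an overnight stay possibly do too.

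The size cannot be given as a number of missed events, because the documents state neither an injury rate nor a survey non-return rate. Section 15a rates the risks low in probability and magnitude, and the EHR utilization data may allow some treated events to be recovered at analysis. No primary estimate depends on the matter. The case rests on a cheap correction, not on an expected large harm. It assumes that no routine check is set out in the appendices that were not available.

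**What to change.** Reconcile Sections 5c and 14 as follows.

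- Name the linked EHR in Section 14 as a routine second adverse-event source for all randomized mothers and infants in both arms, covering treated injuries as well as admissions.
- Run the query before each 6-monthly review already planned in Sections 9a and 14. Supply the extract without arm labels, because Section 9a states: "The programmer/analyst, biostatistician, and investigators will be blinded to the study arms".
- Keep the surveys for untreated events and for exercise-relatedness.
- Use one hospitalization wording throughout Section 14.
- Use no PHI obtained after a participant withdraws authorization, as Section 9a already requires.

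No clinical action rule changes. The cost is programmer time for a recurring query on records the study already plans to link, and an IRB amendment. Section 7f already states: "Parent permission will be obtained for accessing child records and child assent will not be obtained". The consent form itself (Appendix H) was not available, so its wording should be checked against this use. Care outside KPNC would still be missed.

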**MomZing Intervention –** Women in this arm will participate in the online fitness program, including setting physical activity goals, tracking their workouts using the built-in workout tracker on the MomZing website, and playing the exercise videos.

**Control (Usual care) –** Participants in this arm will receive usual postpartum care for women at increased risk of depression, which is currently a brief discussion about their depression symptoms.

To evaluate procedures for implementation of MomZing at KPNC, we will conduct recorded qualitative interviews with clinicians and clinical leaders to help identify a sample of approximately 20 clinicians. Interview recordings will be destroyed at the end of the study.

- Procedures to monitor subjects for safety, including who will review the data and at what frequency for safety issues.

The study team, specifically the project manager, programmer, and research assistant will monitor subjects for safety and assist participants when navigating the surveys and MomZing website, if needed. They will also review adverse event data every 6 months during the data collection period to assess any potential safety issues. The research assistant will also ensure participants, especially at baseline, are properly wearing the accelerometer and answer any questions. Should any issues arise, they will address them, accordingly, including consulting with the PI and Co-Is. The PIs will review all safety data collected at the 3-month (T1) and 6-month (T2) follow-up surveys every 6 months during data collection.

- Procedures performed to lessen the probability or magnitude of risks.

To lessen the probability or magnitude of risks, only the study email address will be used to send and receive participant email. Also, the survey link that will be sent is unique for each participant and thus will minimize any risks as well. Lastly, participants will need to provide their own credentials (date of birth) to authenticate their identities before starting the survey.

- The source records that will be used to collect information about subjects. (Attach all surveys, scripts, and data collection forms.)

Please see the four surveys (baseline, 3 months post-baseline, 6 months post-baseline, and ASQ-3 infant 12-month survey) that will be conducted via REDcap for patient participants (Appendices M-P) and the interview guide for the clinician interviews (Appendix S).

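### No specified step gets an individual serious adverse event reported and read before about the end of the affected woman's 3-month MomZing programme

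*Combined protocol and SAP*

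**What the plan says.** Section 9a fixes the exposure: "Once randomized, participants will begin their assigned group's intervention or control treatment for 3 months". The follow-up surveys count from baseline, with outcomes such as "depressive symptoms at 3 months (T1) and 6 months (T2) post-baseline".

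Section 14 gives the source of safety data, "Adverse event information will be reported by participants as part of follow-up surveys", and its timing, "Adverse event information will be collected as part of the 3-month and 6-month follow-ups surveys". It then sets the review: "Adverse event data will be reviewed by the PIs every 6 months during data collection". Section 9a gives the project manager, programmer and research assistant the same interval: "They will also review adverse event data every 6 months during the data collection period to assess any potential safety issues". The data monitoring committee item is answered as not applicable.

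If a serious event related to exercise is reported, section 14 has the PIs notify the IRB and "remove participants who experience serious adverse events from the study". They would also change the protocol; one such change is given as "increasing adverse event monitoring to include identification of hospitalization events in participants using the electronic health records on a more frequent basis (i.e. monthly".

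Three other places bear on timing:
- Section 5c (Children) says mother and infant records will be used to monitor adverse events, including injuries treated by a doctor, but gives no schedule.
- Section 9a says staff will deal with issues that arise and consult the PI, without a trigger or time limit.
- Section 7a mentions a study phone line and email for questions; it does not present them as a route for reporting events.

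**The concern.** The actions in section 14 are useful only if an event becomes known in time. The first dated report falls at about the end of the assigned programme, and the review interval is twice the programme's length. No faster tier sits beneath the PIs, because the study team works to the same 6-month interval.

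Two groups are exposed to the delay. One is the woman who had the event, for whom removal protects little once her programme is over. The other is the women who start the same programme before anyone has read the report. Section 15a lists exercise injury as foreseeable, the women exercise with their infants, and section 14 counts infant hospitalization as a serious event. A pattern in mothers or infants could go unread while recruitment continues.

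**Working it through.** The plan gives no figure for reporting delay, so there is none to reproduce. The check is timeline arithmetic.

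**Inputs from the documents**
- Assigned programme: 3 months from randomization (section 9a).
- Dated reports: 3 and 6 months post-baseline (section 14).
- Review: every 6 months (sections 9a and 14).
- Enrolment: 08/01/2020 to 03/31/2022 (section 9a), which is 20 months. With 100 women in the MomZing arm, accrual is 100/20 = 5 per month if even.

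**Assumptions**
- Event time U is uniform over the 3 programme months.
- The wait W from report to the next review is uniform on 0 to 6 months, because enrolment is staggered.
- Start dates are uniform over the 20 months.

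**1. Delay from event to review, with baseline and randomization coinciding.** The report comes at month 3 and the review at month 3 + W, so between months 3 and 9, mean 6.
- Maximum delay: 3 + 6 = 9 months.
- Mean delay: 1.5 + 3 = 4.5 months.
- Share of on-programme events reviewed before the programme ends: 0%.

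**2. Randomization g months after baseline.** Section 9a puts at least the 7-day accelerometer wear between the two; mailing time is not stated, so g is an assumption. The programme then ends at month 3 + g. A share (3 − g)/3 of events is reported at T1, and each of these is reviewed in time with probability g/6.
- g = 0.25: 0.917 × 0.042 = about 4%.
- g = 0.5: 0.833 × 0.083 = about 7%.
- g = 1: 0.667 × 0.167 = about 11%.

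A simulation with 1,000,000 draws gave 3.8%, 6.9% and 11.2%, with a mean delay of 4.5 months each time.

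**3. Use continuing to month 6 (not stated in the plan).** For events in the first 3 months, review before month 6 needs W < 3, so 3/6 = 50%. Events in months 3 to 6 are reported at month 6, so none of them is reviewed in time. Over all events the share is 25%.

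**4. Further women starting MomZing between event and review.** For a point a months after a woman's start, truncating at the close of recruitment reduces the mean elapsed time from a to a − a²/40.
- Review, a = 3 + W: mean 6, mean square 36 + 3 = 39, giving 6 − 39/40 = 5.025.
- Event, a = U: mean 1.5, mean square 3, giving 1.5 − 3/40 = 1.425.
- Difference: 3.6 months, and 3.6 × 5 = 18 women.

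**5. The same count if the T1 answer were acted on at receipt.** The end point is a = 3, giving 3 − 9/40 = 2.775. The difference is 2.775 − 1.425 = 1.35 months, and 1.35 × 5 = about 7 women. Prompt reading at T1 thus removes more than half of the interval; only reporting before T1 removes the rest.

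**The case against.** A reader might infer that the protective actions cannot take effect while the affected woman is still exercising. The documents do not support that, for five reasons.

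- Section 5c foresees record-based monitoring of adverse events. Section 14's monthly checks can be read as raising the frequency of something already under way.
- Section 14 triggers the IRB report and the removal when an event is reported. It does not tie them to the 6-monthly review, which answers a template item about cumulative data.
- Section 9a lets staff handle issues as they arise, and a study phone line and email exist.
- T1 counts from baseline and the programme from randomization, so T1 can fall shortly before the programme ends.
- Nothing says MomZing access closes at 3 months.

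In addition, the consent form and the surveys are not available for this review and may ask for earlier reporting. Section 15a rates the physical risks as low, eligibility excludes women with several cardiac and orthopedic risks, and section 14 anticipates no serious events. How often to review in such a trial is partly a matter of judgement.

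All of this limits the claim without removing it. None of these routes carries a schedule, a trigger or a time limit, so none can be counted on to bring an event forward. Low risk bears on how urgent the change is, not on whether the schedule works.

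**Conclusion.** The point holds for the procedures that the plan specifies. Few or no on-programme events would be reviewed before the woman's programme ends: 0% if baseline and randomization coincide, and about 4% to 11% if randomization follows by 0.25 to 1 month (assumed). Delay to review is at most about 9 months, with a mean of about 4.5 under uniform timing. If MomZing use continued to month 6, half of the events in the first 3 months would be reviewed before then.

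About 18 further women on average would start MomZing before the review, given even accrual and no action on any report until then; acting on T1 answers at receipt would bring this to about 7. Larger counts are tempting but should not be used. Multiplying 4.5 months by 5 gives 22.5 women and ignores the end of recruitment. Multiplying 9 by 5 gives 45 and needs a day-one event, the worst review date and open recruitment throughout.

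Sections 5c, 9a and 14 must be reconciled on when records are checked and when a single report is read.

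**What to change.** In sections 9a and 14:

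1. Instruct participants at enrolment to report events that meet section 14's existing definition, in mother or infant, through the existing study phone line or email when they happen. This is the only part that can act before T1.
2. Set a REDCap alert on the T1 and T2 adverse event items so that each positive answer is read on receipt. Section 9a blinds the investigators but not the research assistant, so the alert should go first to the research assistant or the project manager (whose blinding status is not stated), who passes the event to the PIs without naming the arm.
3. State that the 6-monthly review is for cumulative data and that individual serious reports do not wait for it. In the same edit, say whether and when the record monitoring of section 5c takes place.

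The cost is one alert, one line in the participant instructions, slight extra staff handling and an IRB amendment. There is some risk that a PI infers the arm from a single event. No clinical or removal rule changes, and the event definition stays as it is.
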